#### ACT Intervention Procedures

Drs. [name] and [name] developed the ACT manual, which was informed by literature on fatigue and related symptoms in MBC patients, the ACT model, previous ACT trials with cancer patients and other populations with chronic conditions, and [name] extensive experience delivering ACT to cancer patients. In the pilot trial, the intervention addressed the interference of any symptoms with activities. We refined the manual for the current study to focus on fatigue interference because it is the most common concern of MBC patients, and pilot findings were promising with respect to this outcome. The manual is found in Appendix H. Grounded in the ACT model, the intervention is designed to increase psychological flexibility (i.e., full awareness of the present moment, including fatigue, while persisting in actions consistent with personal values) and thereby reduce fatigue interference.

Licensed therapists will deliver the intervention. Table 3 shows a summary of the ACT sessions. While the therapist will aim to hold sessions on a weekly basis for 6 weeks, participants will have up to 12 weeks to complete the 6 sessions. According to the ACT model, psychological flexibility is cultivated through the practice of six psychological skills: acceptance, values, defusion, contact with the present moment, self as context, and committed action. These skills constitute mindfulness and acceptance processes and commitment and behavior change processes. Each session has a primary focus on one of the six psychological skills (see Table 3), although in-session exercises and home practice generally promote multiple skills simultaneously. During the first session, the patient's background and fatigue management strategies will be discussed, and the concept of mindfulness will be introduced. Participants will

complete a 3-item version of the Fatigue Symptom Inventory and a 4-item standardized assessment of anxiety and depressive symptoms at the beginning of each session (see Appendix I). Completion of this assessment will allow the therapist to monitor and respond to participants' fatigue and distress. Paper copies of the questionnaires will be provided to participants to facilitate survey completion. Across the six sessions, patients will practice mindfulness exercises, clarify their values, and set specific goals aligned with their values. Sessions will incorporate discussion of patients' cancer experience, as their energy level and personal goals will be discussed in the context of their current medical care, functional status, and emotional responses to cancer. Each session will include assessing and recording the patient's home practice of mindfulness and other skills and will end with a discussion of practice for the week ahead. Through skill practice, participants will learn new and more adaptive ways to respond to fatigue and other unwanted internal experiences (e.g., anxiety). Handouts summarizing the topics of each session (Appendix J) and a CD that our team developed to guide mindfulness practices will be mailed to participants. Participants will also have the option of receiving the mindfulness recordings via an emailed link from IU Box.

**Table 3. ACT Session Description and Home Practice Assignments**

Topic (Targeted ACT model skill)	Session and Home Practice (HP) Content
Session 1: Introduction to Mindfulness (Acceptance)	
 
Introductions and overview of the intervention
 
Discuss patient's strategies for fatigue management, including control- vs. acceptance-based strategies and the workability of each in the context of coping with cancer
 
Introduce mindfulness and practice mindfulness (noticing sounds around her and her breathing) with therapist
 
HP1: Write a list of ways that fatigue has interfered with living a meaningful life; practice mindful breathing exercise daily; value-based goal
 

Session 2: Exploring What is Most Important to You (Values)	
 
Home practice review
 
Body scan mindfulness exercise and debriefing with reference to fatigue and the cancer experience
 
Clarify patient's values with birthday exercise and explore how patient might respond to fatigue in an adaptive, values-consistent manner
 
Patient rates consistency of actions with values using the Valued Living Questionnaire
 
HP2: Engage in action step in line with values; practice body scan exercise daily and log what is noticed
 

Session 3: Decreasing Emotional Reactivity to Fatigue-related Thoughts and Emotions (Defusion)	
 
Practice "leaves on the stream" mindfulness with therapist
 
Home practice review
 
Discuss the patient's attempts to suppress the experience of fatigue and cancer-related thoughts and emotions (e.g., living with uncertainty) and the costs of these attempts in terms of reduced QoL
 
Explore the difference between "having" a thought and "buying" a thought
 
Further practice of mindfulness (noticing object or scene) with therapist
 
HP3: Write down two activities given up due to fatigue and any resulting emotions; practice "leaves on a stream" mindfulness exercise daily; value-based goal
 

Session 4: Mindful Awareness of Fatigue (Contact with the Present Moment)	
 
Practice mindfulness (noticing environment) with therapist
 
Home practice review
 
Practice mindful breathing
 
Introduce concept of willingness (i.e., flexibly making contact with the present moment, including fatigue)
 
HP4: Write down two activities that were enjoyed even while fatigued and resulting emotions; practice mindful breathing exercise daily; value-based goal
 

Session 5: Detaching from Fatigue (Self as Context or Perspective-Taking)	
 
Practice mindfulness (self-compassion exercise) with therapist
 
Home practice review
 
Discuss observing and detaching from fatigue and related thoughts and emotions to cultivate a transcendent sense of self from which to observe and accept changing experience
 
Discuss letting go and accepting things as they are
 
HP5: Goal setting and practice; daily mindfulness practice (patient's choice on CD)
 

Session 6: Taking Steps to Do What Matters to You (Committed Action)	
 
Practice mindfulness (brief body scan exercise) with therapist
 
Home practice review
 
Recap of skills and what patient learned
 
Goal setting around expanding patterns of values-consistent behavior after the study ends
 
Practice mindfulness (self-compassion exercise) with therapist
 
Termination and next steps in the study
 
HP6: Continue written goals
 

### Education/Support Condition Procedures

The education/support control condition was tested in our pilot feasibility study. The manual is found in Appendix K. Patients randomized to the education/support condition will discuss their concerns, including symptoms and other cancer-related stressors, with a therapist providing psychological support. The therapist will direct patients to resources for practical and health information and contact information for psychosocial services. Thus, this study tests whether ACT is superior to supportive listening and education regarding medical center and community resources, consistent with common

interventions in clinical settings.

Licensed therapists will deliver the education/support intervention. Table 4 provides a summary of the sessions. While the therapist will aim to hold sessions on a weekly basis for 6 weeks, participants will have up to 12 weeks to complete the 6 sessions.

Education/support participants will complete the same weekly fatigue and distress assessments as those in the ACT condition. Sessions will include an orientation to the patient's medical center and treatment team, education regarding common QoL concerns and symptoms experienced by cancer patients, and an overview of medical center and community resources for addressing these concerns.

Therapists will also describe resources for addressing financial

concerns and methods of evaluating health information available via the Internet and other modalities. Education/support participants will receive handouts summarizing the topics of each session and will be asked to review them as homework (Appendix L). ACT concepts will not be discussed in the education/support condition; thus, there is no overlap in intervention content between study conditions.

### Training of Therapists and Treatment Fidelity

Training of therapists will involve didactics, live demonstrations, and role plays developed by the PI and her collaborators. All intervention sessions will be audio recorded, and the PI and [name] (study consultant and licensed clinical psychologist) will randomly review 20% of recorded sessions to ensure fidelity and quality control. The PI will use therapist adherence checklists for the ACT and education/support conditions adapted from NIH-funded trials with

Table 4. Education/Support Session Description and Homework	
Topic	Session and Homework (HW) Content
Session 1: Orientation to medical center and treatment team; Overview of QoL issues	
 
• Overview of the upcoming sessions
 
• Orientation to the medical center
 
• Overview of components of QoL and discussion of physical QoL and symptoms
 
• Discuss educational materials from the healthcare team
 
• Overview of treatment team
 
 HW1: Review handouts on medical center information
Session 2: Resources for addressing social functioning	
 
• Review common social challenges such as talking with children about cancer and employment issues
 
• Contact information for resources to address social challenges
 
 HW2: Review handouts on contact information for resources to address social challenges
Session 3: Resources for addressing role and emotional functioning	
 
• Tips on managing common household challenges when ill
 
• Review common emotional responses to cancer, including anxiety and depressive symptoms, and cognitive changes following cancer treatment
 
• Contact information for mental health services
 
 HW3: Review handouts on contact information for mental health services
Session 4: Resources for addressing financial concerns	
 
• Review common financial concerns related to cancer and its treatment
 
• Contact information for resources to address concerns
 
 HW4: Review handouts summarizing resources for addressing financial concerns
Session 5: Resources for evaluating health information	
 
• Review methods of evaluating health information on the Internet and other modalities
 
• Discuss resources for evaluating health information
 
 HW5: Review handouts summarizing resources for evaluating health information
Session 6: Review and further resources	
 
• Review all topics discussed in prior sessions and available resources for addressing each topic area
 
• Discuss websites for accessing cancer-related information
 
 HW6: Review handouts summarizing all resources

cancer patients (see Appendix M). The PI and [name] will provide ongoing supervision of therapists. During individual supervision with therapists, which will occur approximately every 1-2 weeks, treatment adherence scores will be provided and treatment fidelity issues discussed. Role-plays will be conducted to correct deviations from study procedures.

## 7.0 Statistical Considerations

Design and data considerations. The primary and secondary outcomes in the proposed study are scaled continuously. For these outcomes, a linear mixed model using the SAS procedure MIXED will be employed. Because parameter estimation in MIXED employs full information maximum likelihood, all data the individual provides are included in the analysis even if some of the data are missing.

Preliminary analyses: Distributional issues. Univariate and descriptive analyses will be performed on all dependent variables, and if necessary, normalizing and/or variance stabilizing transformations will be sought in the family of power transformations and applied to the data before inferential analyses are undertaken. Missing data/subject attrition. We anticipate some missing data due to participant death, medical factors, and other reasons. For individuals who complete the first assessment but withdraw from the study, we will examine demographic, medical, and symptom factors that might be predictive of dropout using logistic regression. In the analyses for the primary and secondary objectives described below, all randomized participants will be included in intent-to-treat analyses, as the aims are concerned with the impact of the intervention on outcomes regardless of study completion status. Second, for participants who miss assessments, it is possible that attrition may be related to the study condition to which they have been assigned. We plan to use the random effects pattern-mixture model proposed by Hedeker and Gibbons to address missing data. Analyses of potential covariates. Because patients will be randomly assigned to the two study conditions, significant differences on the baseline values of all measured variables are not expected. T-tests and chi-square analyses will be performed to determine whether there are differences between the groups on potential baseline covariates (e.g., demographic and medical variables), and if there are differences these variables will be used as covariates in subsequent analyses.

Primary objective (2.1): To test the effect of telephone-based ACT on fatigue interference in MBC patients. A linear mixed-model repeated measures approach (SAS Proc-Mixed) will be used to test the hypothesis (#1) that ACT will improve fatigue interference as compared to the education/support condition. The model will include the main effect of time (as categorical) and study group (ACT vs. education/support) and the time-by-study group interaction. A treatment effect will be evidenced by a significant interaction between time and study group. If the treatment effect is significant, follow-up tests will be conducted to examine group differences at each follow-up, controlling for the outcome at baseline.

Statistical power. Our sample size is calculated based on the estimated difference between study conditions (ACT vs. education/support) on the primary outcome of fatigue interference at 2 weeks post-intervention. In our pilot study, we found a moderate effect ( $d = -.30$ ) of study condition on fatigue interference at 1 month post-intervention. It should be noted that only about half of the pilot sample had elevated fatigue interference at baseline (unlike the proposed study, the pilot study did not require all eligible patients to have clinically significant levels of fatigue interference); thus, the effect size is likely to be higher in the proposed study where the sample will have uniformly elevated fatigue interference at study entry. Indeed,

among patients with moderate to severe baseline fatigue interference in our pilot study, we found a strong effect ( $d = -.59$ ) of study condition on fatigue interference at 1 month post-intervention. Thus, we conservatively estimate a medium effect size of  $d = -.40$  at 2 weeks post-intervention. With a sample size of 198 patients at 2 weeks post-intervention (assuming 21% attrition), we will have 80% power ( $p = .05$ , two-tailed) to detect a Cohen's  $d$  of  $-.40$  in a linear mixed model. At the final, 6-month follow-up with a sample size of 163 (assuming 35% attrition), we will have 80% power ( $p = .05$ , two-tailed) to detect a Cohen's  $d$  of  $-.44$ .

Secondary objective (2.2a): To test the effects of telephone-based ACT on secondary outcomes in MBC patients. Linear mixed models will be run in SAS Proc-Mixed to test the hypothesis (#2) that ACT will improve sleep interference, engagement in daily activities, and QoL as compared to the education/support condition. Each model will include the main effect of time (as categorical) and study group and the time-by-study group interaction. A treatment effect will be evidenced by a significant interaction between time and study group. Probabilities for secondary outcomes will be Sidak adjusted for correlated multiple outcomes to control the familywise Type I error rate. If treatment effects are significant, follow-up tests will be conducted to examine group differences at each follow-up, controlling for the outcome at baseline.

Secondary objective (2.2b): To examine change in psychological flexibility as a mediator of ACT's effect on fatigue interference. The PROCESS macro for SAS developed by Andrew Hayes will be used to test the hypothesis (#3) that increases in psychological flexibility will mediate the effect of ACT on fatigue interference. This analysis employs ordinary least squares regression. Bootstrapped confidence intervals will be computed for the indirect effect of study group on fatigue interference at 2 weeks post-intervention (via change in psychological flexibility over the same time period). The analysis will control for baseline levels of the mediator and outcome. We will also compute the indirect effects of study group on fatigue interference at 3 and 6 months post-intervention (via change in psychological flexibility at 2 weeks post-intervention). These analyses will also control for baseline levels of the mediator and outcome.

Exploratory objective (2.3): To explore changes in the two core aspects of psychological flexibility (i.e., mindfulness/acceptance and commitment/behavior change) as mediators of ACT's effect on fatigue interference. The PROCESS macro for SAS will be used to explore the extent to which changes in mindfulness/acceptance and commitment/behavior change processes mediate the effect of ACT on fatigue interference. Both potential mediators will be entered into the same model. Bootstrapped confidence intervals will be computed for the indirect effect of study group on fatigue interference at 2 weeks post-intervention (via change in mindfulness/acceptance and commitment/behavior change processes over the same time period). The analysis will control for baseline levels of the mediators and outcome. We will also compute the indirect effects of study group on fatigue interference at 3 and 6 months post-intervention (via changes in mindfulness/acceptance and commitment/behavior change processes at 2 weeks post-intervention). These analyses will also control for baseline levels of the mediators and outcome.

Other exploratory analyses. To inform future research, we will explore the extent to which sociodemographics (e.g., age, education) and clinical characteristics (e.g., cancer treatments, baseline fatigue severity) moderate the effects of ACT on primary and secondary outcomes. For

these analyses, we will use linear mixed modeling at a two-sided significance level of 0.05. Preliminary findings or hypotheses generated from these moderation analyses will be further tested in a future trial.

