## 5.0 Enrollment/Randomization

Following baseline assessments, patients ( $N = 250$ ) will be randomly assigned to the ACT intervention or education/support condition using a stratified block randomization scheme to balance the groups by patient age (<65 vs.  $\geq 65$  years) and performance status (Eastern

Cooperative Oncology Group scores 0 or 1 vs. 2). We will stratify randomization by performance status because the decision to provide chemotherapy and other cancer treatments is often based on performance status. Randomization will be performed by the IU Biostatistics Department. The study statistician will create the randomization procedure, and the PI will inform study therapists of their assigned patients. Other members of the study team will remain blind to participants' group assignment. All patients will be registered with the Indiana University Cancer Center Clinical Trials Office. Applicable regulatory documents must be completed and on file prior to registration of any patients.

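### Covariates are chosen by between-arm baseline tests and the two randomisation strata are in no primary or secondary model; the effect is minor and the fix nearly free

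*Combined protocol and SAP*

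**What the plan says.** Section 7.0 (Analyses of potential covariates) first states that, because of randomisation, "significant differences on the baseline values of all measured variables are not expected". It then runs t-tests and chi-square tests between the arms on possible baseline covariates, with demographic and medical variables named as examples, and adds: "if there are differences these variables will be used as covariates in subsequent analyses".

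Section 5.0 assigns patients "using a stratified block randomization scheme to balance the groups by patient age" (<65 vs ≥65 years) and by performance status (0 or 1 vs 2). It gives a clinical reason for the second factor: "We will stratify randomization by performance status" because treatment decisions often depend on it.

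The primary model in section 7.0 contains time, group and their interaction, and the criterion is: "A treatment effect will be evidenced by a significant interaction between time and study group". For the secondary outcomes, "Each model will include the main effect of time (as categorical) and study group and the time-by-study group interaction". Per-visit comparisons are conditional: "If the treatment effect is significant, follow-up tests will be conducted to examine group differences at each follow-up". They adjust for the baseline value of the outcome. The mediation regressions (objectives 2.2b and 2.3) adjust for baseline mediator and outcome and are not made conditional on a significant interaction. No stratum is a prespecified term in any of these models. Section 7.0 names age only as a possible moderator in the exploratory analyses.

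**The concern.** By the plan's own reasoning, a baseline difference between randomised arms is chance. A rule that adjusts for whatever differs therefore selects on accident. A strongly prognostic variable that happens to balance stays out, and an irrelevant one that happens to differ goes in. Because the candidate list is open, nobody can write down today the model that will be fitted.

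The factors the design treated as important enough to stratify on are the ones this rule is least able to select. At stake are a fixed, reproducible covariate set and possibly a little power.

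**Working it through.** **1. The plan's own figure.** Inputs from section 7.0: d = .40, two-sided .05, 80% power, 21% and 35% attrition from N = 250. Assumed: 1:1 allocation, SD = 1.

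- Retained: 250 × 0.79 = 197.5 and 250 × 0.65 = 162.5, which agree with 198 and 163.
- n per arm = 2(1.960 + 0.842)²/0.40² = 98.1, so 99 per arm and N = 198.
- Power at 198 = Φ(0.40 × √198/2 − 1.960) = Φ(0.854) = 80.4% (80.0% with the t distribution).
- For d = .44 the same formula gives 164 against the stated 163; power at 163 is 80.2% (79.7% with t).

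The calculation reproduces and is not in dispute.

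**2. How often chance picks a covariate.** With k independent tests at .05, the chance of at least one selection is 1 − 0.95^k: 34%, 54% and 79% for k = 8, 15 and 30. The value of k is an assumption, because the list is open.

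**3. Whether the rule can pick the strata.** In 64,000 simulated stratified-block randomisations (30% prevalence per factor and blocks of 4, 6 or 8, all assumed) neither stratum was ever selected; the smallest p-value was .43. Age tested as a continuous variable was selected in 0.3%.

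**4. What the rule changes.** With complete data, a covariate entered as a main effect does not alter the time-by-group test, because it cancels in within-patient change. The rule therefore acts on the follow-up contrasts and the mediation regressions. For the 2-week contrast, counted only when the interaction is significant (n = 198, correlation .5, 15 independent candidates jointly explaining 2 to 30% of variance, all but n assumed), the p < .05 verdict changes in 1.0 to 1.8% of trials at d = .40. With 8 to 30 candidates the range is 0.7 to 2.3%, and with no effect it is 0.5% or less.

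With no effect, a significant interaction followed by p < .05 at 2 weeks occurs in 1.3 to 1.7% of trials without the rule and 1.0 to 1.6% with it. In simulations with 10 candidates the mean estimate under the rule was 0.396 to 0.403 for a true 0.40, and −0.003 to 0.000 for a true zero. The effect on the mediation regressions was not quantified.

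**5. Strata omitted, time-by-group test.** Assumed: d = .40 at all three follow-ups and strata explaining 5, 10 or 15% of follow-up variance. Gain in power from adding strata with stratum-by-time terms:

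| Strength of strata at baseline relative to follow-up | Gain in points at 5 / 10 / 15% |
|---|---|
| Equal | about 0 (0.2 / 0.3 / 0.7 with dropout) |
| Three-quarters | under 1 |
| Half | 0.3–0.5 / 0.8–1.0 / 1.7–1.9 |
| None (extreme) | 2.3–2.6 / 4.5–4.9 / 6.7–7.7 |

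Ranges span repeated simulations. The middle two rows use complete data for 198. The first and last also use N = 250 with 21/28/35% cumulative loss (28% at 3 months is assumed). Type I error with dropout was 4.2 to 5.9% without the strata terms and 4.8 to 5.7% with them.

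**6. Strata omitted, per-visit contrast.** Let R² be the assumed share of endpoint variance explained by the strata, with N = 198 and d = .40.

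- Included: power = Φ(d√N / (2√(1−R²)) − 1.960).
- Omitted: power = Φ((d√N/2 − 1.960)/√(1−R²)); type I error = 2[1 − Φ(1.960/√(1−R²))].

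| R² | Type I, omitted | Power, omitted | Power, included | Gain (unrounded inputs) |
|---|---|---|---|---|
| .02 | .048 | 80.6% | 81.1% | 0.5 |
| .05 | .044 | 81.0% | 82.3% | 1.4 |
| .10 | .039 | 81.6% | 84.3% | 2.7 |

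The planned contrasts already adjust for the baseline outcome, so the extra R² is probably at the low end.

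**The case against.** The strongest reply is that nothing important breaks. Randomisation protects the estimate, the main test is barely touched, and a verdict flips in about 1 to 2% of trials under assumptions that are partly arbitrary. The only sizeable power gain needs age and performance status to predict fatigue interference after baseline but not at baseline. Both are known before randomisation, and the documents give no reason to expect that pattern. All of this stands, and it is why the point is graded minor.

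A reader might infer more in four ways, none supported by the documents:

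- *Test-then-adjust inflates false positives or biases the effect.* With a fixed threshold it does neither. In a per-visit contrast, omitting the strata makes the test slightly conservative.
- *The sample size is wrong.* It reproduces, and it does not rely on covariates.
- *The trial loses seven or eight points of power.* That is the extreme corner of an assumed range. The documents do not show whether the strata predict change at all.
- *There is no threshold at all.* The rule states none, but the same paragraph speaks of significant differences, and .05 two-sided is the only level used in section 7.0 (for the moderator analyses, "we will use linear mixed modeling at a two-sided significance level of 0.05").

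What the reply does not answer is that the covariate set is unknown until baseline data are seen, in the mediation regressions as well as the follow-up contrasts, and that a fixed alternative costs almost nothing.

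**Conclusion.** The point holds as a minor one that should be corrected. Covariates for later analyses are decided by chance imbalance from an open list, and the two stratification factors are in no primary or secondary model. The expected gain in the primary test from including them is near zero to about 2 points. In the per-visit contrasts it is about 0.5 to 3 points at an assumed 2 to 10% of variance, probably nearer the bottom. These sizes rest on assumptions the documents do not supply: variance explained by the strata, correlation .5, prevalence of each stratum, number of candidates, and d = .40 held at every follow-up (section 7.0 assumes it only at 2 weeks). The main reason to change is that the analysis becomes fully specified in advance; any added power is secondary.

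**What to change.** - Delete the rule that tests baseline variables and then adjusts for those that differ.
- Prespecify age group and performance status, as used at randomisation, in every primary and secondary mixed model, with stratum-by-time terms. Main effects alone would hardly move the time-by-group test.
- Add both factors as covariates in the baseline-adjusted follow-up contrasts and in the mediation regressions.
- Keep the time-by-group interaction as the test of treatment effect.
- Report baseline characteristics by arm descriptively, without p-values.
- Put any further adjustment in a sensitivity analysis with a closed covariate list.

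The cost is a few sentences of SAP text and, with four visits, about eight model degrees of freedom: 2 main effects plus 2 × 3 stratum-by-time terms. Both factors must be known to assign the strata, so no new data, visits or patients are needed.

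### The primary and secondary models and the 80% power make no allowance for therapist clustering; if therapists are nested in arm, the 5% test rejects too often and the power is overstated

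*Combined protocol and SAP*

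**What the plan says.** Patients are randomised individually, with strata for age and performance status only (section 5.0). After randomisation, "the PI will inform study therapists of their assigned patients". Both conditions consist of six one-to-one telephone sessions. For ACT, "Licensed therapists will deliver the intervention"; for the control, "Licensed therapists will deliver the education/support intervention". Section 6.0 adds shared training, review of 20% of recorded sessions, and supervision about every one to two weeks.

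For the primary outcome, section 7.0 specifies: "The model will include the main effect of time (as categorical) and study group (ACT vs. education/support) and the time-by-study group interaction". A significant interaction is the evidence of a treatment effect. The secondary outcomes use the same terms, and the mediation analysis uses ordinary least squares.

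On power, the plan states: "With a sample size of 198 patients at 2 weeks post-intervention (assuming 21% attrition"), "we will have 80% power ( $p = .05$ , two-tailed") to detect d = −.40. At 6 months, "with a sample size of 163 (assuming 35% attrition"), it gives the same power for d = −.44.

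Section 7.0 has no therapist effect, ICC, design effect or therapist sensitivity analysis. The documents do not state how many therapists there are, how patients are allotted to them, or whether a therapist delivers one condition or both.

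**The concern.** Patients who share a therapist share that therapist's skill and style, so their post-treatment outcomes may be correlated. The mixed model can deal with repeated measures within a patient, but as described it has nothing at the therapist level. If each therapist works in one arm only, differences between therapists become part of the difference between arms, and a standard error computed from independent patients leaves that variance out. The same happens if therapists work in both arms but differ in how much ACT helps their patients. The nominal 5% test of the main hypothesis then rejects too often, and a test that corrects for this has less power than stated.

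**Working it through.** **Inputs from section 7.0.** Two-sided α = .05. N = 198 at 2 weeks (250 × .79 = 197.5), d = .40. N = 163 at 6 months (250 × .65 = 162.5), d = .44. The allocation ratio is not stated; 1:1 is assumed, so 99 per arm at 2 weeks.

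**Assumptions not in the documents.** k = 2, 3 or 5 therapists per arm, nested in arm; ICC = .01, .02 or .05; correlation ρ between visits of .3 to .7; complete data; a therapist effect that starts after baseline and is the same at all three follow-ups.

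**1. The plan's figure.** Power = Φ(d/√(2/n) − 1.96).
- 2 weeks: .40/√(2/99) = 2.814, so Φ(0.854) = 80.3%.
- 6 months, n = 81.5: 80.2%.

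Both reproduce with independent patients, so no allowance for clustering is built in.

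**2. Power of a 2-week test that allows for clustering.** Patients per therapist m = 99/k; design effect DE = 1 + (m − 1) × ICC; power = Φ(2.814/√DE − 1.96).

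| ICC | k = 2 (m = 49.5) | k = 3 (m = 33) | k = 5 (m = 19.8) |
|---|---|---|---|
| .01 | DE 1.485, 64% | DE 1.320, 69% | DE 1.188, 73% |
| .02 | DE 1.970, 52% | DE 1.640, 59% | DE 1.376, 67% |

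These figures use normal quantiles. With a t reference on 2(k − 1) degrees of freedom, power at ICC .01 is 27% for k = 2 and 46% for k = 3.

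**3. Type I error of the stated 3-df interaction test.** The test uses the between-arm differences in change from baseline at three follow-ups. With outcome variance 1, a therapist share equal to the ICC, and correlation ρ in the remainder, the patient-level covariance of the changes is (1 − ICC)(1 − ρ)(I + J) + ICC·J, where I is the identity and J the matrix of ones. Nesting adds (m − 1)·ICC·J, which inflates only the component common to the three visits, by

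λ = 1 + 3(m − 1)·ICC / [4(1 − ICC)(1 − ρ) + 3·ICC].

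In large samples the type I error is P(λχ²₁ + χ²₂ > 7.815), with independent chi-squares. With λ = 1 this returns 5%.

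| ICC | Lowest (k = 5, ρ = .3) | Highest (k = 2, ρ = .7) |
|---|---|---|
| .01 | λ 1.20, 6.3% | λ 2.20, 13.6% |
| .02 | λ 1.40, 7.7% | λ 3.35, 21.5% |
| .05 | λ 2.00, 12.1% | λ 6.64, 36.8% |

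The ranges are therefore about 6–14%, 8–21% and 12–37%.

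**4. Therapists in both arms.** In a simulation of a single-visit comparison (96 per arm, 8,000 runs per scenario, 2 or 4 therapists, ICC .01 and .05), balanced crossing with no variation of the effect by therapist gave type I error of 4.6–5.0% and power of 79–80%. Nested therapists at ICC .01 gave type I error of 11.1% (2 per arm) and 8.1% (4 per arm).

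**The case against.** The strongest reply is that harm is not shown. Therapist number, caseload, ICC and nesting are all unstated, and step 4 shows none when therapists treat in both arms in balance with a uniform effect. Joint training and supervision may also keep therapist variance small. This stands. A reader might infer that the 5% test is certainly inflated, or that several therapists each carry a large caseload; the documents support neither. The reply does not close the matter, because nothing in the plan commits to crossing or balance, and therapist is not a stratum.

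A second tempting inference is that the planned analysis itself has only 64–73% power. It does not: those figures belong to a corrected test. The uncorrected 2-week test has power Φ((2.814 − 1.96)/√DE), which is 76–78% at ICC .01 and 73–77% at .02. Its main defect is type I error.

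Third, section 7.0 lists fixed effects and gives no random effects or covariance structure at all, even for patient. A therapist effect is unmentioned rather than expressly excluded.

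Fourth, adjusting for baseline could recover power. With an assumed baseline correlation of .5, power is 83% at DE 1.24 and 76% at DE 1.49. That calculation is favourable, since it shrinks therapist variance along with patient variance. The plan does not claim the gain, and it does not repair type I error.

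**Conclusion.** The point holds in conditional form. It is established that the plan has no therapist term and that its 80% power assumes independent patients. Whether this does harm depends on three facts the documents leave out: the number of therapists, the ICC, and nested or crossed delivery. Under nesting with 2 to 5 therapists per arm, even an ICC of .01 puts the primary test at about 6–14% instead of 5% and a corrected 2-week test at 64–73% power; both worsen as the ICC rises. Under balanced crossing with a uniform effect there is nothing to correct. This is a cheap improvement to the plan and does not show that the trial's main test is invalid.

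**What to change.** - Record the therapist's ID for every patient. State the number of therapists, how patients are assigned to them, and whether each delivers one condition or both.
- Pre-specify an analysis of the primary and secondary outcomes with a therapist effect that acts on post-baseline visits: a random therapist-by-time effect, or a random therapist effect in a baseline-adjusted model. Add therapist-by-arm if therapists treat in both arms. Use Kenward-Roger degrees of freedom. A therapist intercept constant over all visits is not enough, because it largely cancels from the change-from-baseline contrasts that the interaction tests.
- If therapists are too few to estimate the variance, keep the stated model as primary and report a sensitivity analysis with the confidence interval widened by √DE for ICC .01 to .05. With 3 nested therapists per arm and 99 patients per arm, the multipliers run from √1.32 = 1.15 to √2.60 = 1.61.
- Restate the 80% power as assuming no therapist clustering, and give the range above with its assumptions.

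The cost is one recorded variable, SAP wording and some model code; sample size and conduct do not change. The downsides are a wider interval, an imprecise variance estimate when therapists are few, and a less favourable stated power.
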